Blumchen et al 2010 [9]	23	3-14	Randomized, open label	7.8% of doses during rush protocol, 2.9% of doses during maintenance	8 (35%)	1 during rush protocol, 7 during long term buildup of which 4 for allergic side effects
Varshney et al 2011 [11]	19	1-16	Double blind, placebo controlled	47% subjects with "clinically relevant" AEs during initial escalation day, 1.2% doses during build up	3 (16%)	2 withdrew during initial escalation day and 1 after first build up dose
Anagnostou et al	22	4-18	Open label	86% subjects during build up and maintenance	1 (5%)	Withdrew after the first up dose at home

2011 [12]						
Anagnostou et al 2014 [13]	99	7-16	Randomized, placebo controlled cross over	6.3 % of all doses	7 (7%)	5 withdrew for allergic reactions or persistent symptoms, 1 disliked taste, and 1 no specific reason
Vickery et al 2014 [14]	39	1-16	Open label	Previously reported in pilot study (Jones et al 2009)	15 (38%)	6 withdrew due to allergic side effect and 9 for personal reasons
Narisety et al 2014 [15]	21	7-13	Randomized, double blind, placebo controlled	43% doses during blinded phase (escalation and maintenance), 36.7% doses in OIT group during unblended phase	7 (33%)	1 withdrew after initial escalation, 1 during build up and 3 during maintenance. 1 drop out on SLIT with placebo OIT
Vickery et al 2016 [16]	37	9-36 months	Randomized, double blind, low and high dose	95% patients during entire study, 0.8% doses during study	5 (14%)	2 withdrew for nonadherence, 1 for recurrent emesis and 1 for EoE

Abbreviations: N, number of subjects, AEs, adverse events, SLIT, sublingual immunotherapy, OIT, oral immunotherapy, EoE, eosinophilic esophagitis

Given the high rate of these treatment related AEs such as oral itching, stomach upset and other GI complaints, and occasional serious systemic allergic reactions requiring the use of injectable epinephrine, OIT is still considered an experimental treatment. While some major medical centers and a number of private practice allergists offer peanut OIT to their patients, it is not yet FDA approved.

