2.3 Risk/Benefit Assessment

2.3.1 Known potential risks

There is a significant rate of adverse reactions with peanut oral immunotherapy in clinical trials to date. Mild adverse reactions such as oral itching or nausea are reported in up to 10-15% of all doses. Over the course of an individual study, this reaches nearly 100% of all subjects. The rate of these adverse events are outlined in representative studies in Table 1.

More severe reactions requiring treatment with epinephrine or inhaled beta-agonists are less frequent but can occur. In a large review of multiple centers performing peanut OIT, Wasserman et al noted a total of 95 adverse reactions requiring epinephrine in 352 patients that collectively received more than 240,000 doses of peanut.²⁵ The results of the largest peanut OIT trial to date, a phase 2 clinical trial utilizing product AR101 were published in March of 2018.²¹ In this study, 9 (14%) of 63 subjects received a single injection of epinephrine during initial double blind placebo controlled food challenge (DBPCFC) at screening: 4 were randomized to AR101, 4 to placebo, and 1 was not enrolled. For the duration of maintenance therapy, one treatment subject received a single epinephrine injection for moderate anaphylaxis at home. Finally, during the exit DBPCFC, 11 of 26 placebo subjects (42%) were administered epinephrine and 2 of 23 AR101 subjects (9%) received a single injection of epinephrine.

Across the various peanut OIT trials, there has been no specific statistical analysis examining adverse reaction rate or withdrawal rate at various ages. Presumably this is due to the fact that no specific age related pattern has emerged and that anaphylaxis and subject withdrawal has occurred in subjects of all ages.

There is also a risk for development of Eosinophilic Esophagitis (EoE). A recent review estimated the prevalence across the OIT clinical trials as 3-4% and in the study conducted by Bird et al, EoE occurred in only 1 subject (<5%) from the treatment group.²¹ Once OIT is discontinued in these patients, the EoE typically resolves.

There is also a risk of causing anxiety or stress in the subject or the family. The impact of oral immunotherapy on quality of life has been examined with a variety of foods. Quality of life in patients with food allergy improves in some but declines in others while undergoing OIT, and in particular tends to decline in those rating a higher quality of life prior to initiation of the treatment.²⁶

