7.1 Discontinuation of Study Intervention

Criteria for discontinuing oral immunotherapy in a subject will include:

- Subject nonadherence to OIT, specifically defined by 12 (approximately 10%) nonconsecutive missed doses.
- A life-threatening adverse reaction to OIT, specifically a grade 4 reaction as defined by the Consortium of Food Allergy Research (CoFAR) criteria. See table in Section 8.3.3.1.
- Symptoms suggestive of Eosinophilic Esophagitis (EoE) – i.e. difficulty swallowing, chest pain, persistent heart burn, upper abdominal pain, and/or no response to gastroesophageal reflux disease (GERD) medication

Symptoms suggestive of Eosinophilic Esophagitis (EoE) will prompt discontinuation of oral immunotherapy and begin once weekly symptom monitoring phone calls with study staff. If symptoms fail to resolve after 1 month off therapy, consultation with Gastroenterology will be considered for further evaluation and management.

Discontinuation from oral immunotherapy does not mean discontinuation from the study, and remaining study procedures should be completed as indicated by the study protocol. If a clinically significant finding is identified (including, but not limited to changes from baseline) after enrollment, the investigator or qualified designee will determine if any change in participant management is needed. Any new clinically relevant finding will be reported as an adverse event (AE).

The data to be collected at the time of study intervention discontinuation will include the following:

- Skin prick test to peanut
- Peanut sIgE, peanut component panel, and peanut IgG4

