8.3.8 Events of Special Interest

This is not applicable to our study.

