9.2.3 Derivation of Safety Variables

Adverse events (AEs) will be categorized by preferred term using the CTCAE Version 5.0, and by the specific AEs of interest listed in section 5.2. The *specific AEs of interest* with possible alternative preferred terms, which will be grouped together, are: oral itching (oral pruritus), rhinorrhea (allergic rhinitis or rhinorrhea), conjunctivitis (eye itching), urticaria (hives), angioedema, abdominal upset (dyspepsia or nausea), vomiting, diarrhea, cough, wheeze (wheezing), and anaphylaxis.

Mortality. Mortality will be identified by an AE of CoFAR severity grade 5, and/or 'Death' indicated as a SAE criteria on the CRF for AEs.

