11.1.2 Comparative AE table

AE data from this study will be compared descriptively to the AE data from three published studies: the study medication arms of the Phase 2 and Phase 3 trials of AR101 OIT for peanut allergy (Bird et al., 2018; Vickery et al. for PALISADE, 2018), and OIT data from the PACE meta-analysis study of OIT for peanut allergy (Chu et al., 2019). No hypothesis testing will be performed.

For this table, study AEs will be categorized into two study phases as best corresponds to the comparative data: 1) initial dose escalation study visit, and 2) an increasing dose phase which includes all other dose escalation study visits and home doses, but excludes the exit DBPCFC. AEs will be grouped into severity grades, treatments, and preferred terms, where the preferred term list will include the specific AEs of interest only (see sections 5.2 and 9.2.3). (Refer to mock Table 3.3 for comparative data and source information.)

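### The adverse event comparison with roasted peanut OIT has no row for eosinophilic esophagitis, a risk the protocol names and a reason to stop treatment

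*SAP*

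**What the plan says.** **Risk.** Protocol 2.3.1 states: "There is also a risk for development of Eosinophilic Esophagitis (EoE"). It continues: "A recent review estimated the prevalence across the OIT clinical trials as 3-4" percent. Of the AR101 phase 2 trial it says that "EoE occurred in only 1 subject (<5%) from the treatment group". Table 1 in protocol 2.2 gives, among the withdrawals in a 37-subject early-childhood trial, "1 for recurrent emesis and 1 for EoE".

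**Action during the trial.** Protocol 7.1: "Symptoms suggestive of Eosinophilic Esophagitis (EoE) will prompt discontinuation of oral immunotherapy and begin once weekly symptom monitoring phone calls with study staff". If symptoms have not resolved after a month off therapy, referral to gastroenterology is to be considered. No diagnostic procedure is required. The same section says that stopping OIT does not mean leaving the study.

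**Analysis.** SAP 5.2 repeats the eleven side effects listed in protocol section 3. SAP 9.2.3 attaches grouping terms to them, and its list ends: "abdominal upset (dyspepsia or nausea), vomiting, diarrhea, cough, wheeze (wheezing), and anaphylaxis". EoE is not on the list. SAP 11.1.2 sets the trial beside the AR101 phase 2 and phase 3 trials and a meta-analysis, without hypothesis tests. For that table, "the preferred term list will include the specific AEs of interest only (see sections 5.2 and 9.2.3"). It also groups events by severity grade and treatment, within two study phases.

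**The concern.** The secondary objective is to compare the harms of boiled peanut OIT with published harms of roasted peanut OIT, and Table 3.3 is where that comparison is made. Its term list leaves out, by a stated rule, a harm that the protocol regards as known, quantifies from published trials and acts on in individual children. One comparator has an EoE case that the protocol itself cites.

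A reader of Table 3.3 alone could not tell whether EoE was absent or simply not tabulated. The point affects one descriptive table. The primary analysis and every hypothesis test are untouched.

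**Working it through.** **Plan's own figure.** The documents give no figure for how EoE will be analysed. The only design figure is power above 90% with 10 patients, 80% against 20%. It reproduces: at one-sided 0.05 the exact rule is at least 5 of 10 responders, with attained alpha 0.0328 and power 0.9936. Nothing below depends on it.

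**Step 1: where a recorded EoE term would appear.**

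| Table | Term list in the SAP | EoE named? |
|---|---|---|
| 3.1, 3.2 (SAP 11.1.1) | AEs of interest plus any other recorded term | Yes, if recorded |
| 3.4 (SAP 11.1.3) | All recorded terms, serious events excluded | Yes, if recorded and not serious |
| 3.5 (SAP 11.2.2) | All recorded terms meeting serious criteria | Yes, if recorded and serious |
| 3.3 (SAP 11.1.2) | AEs of interest only | No |

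**Step 2: where a suspected case recorded only as symptoms would appear in Table 3.3.** Protocol 7.1 names four symptoms, besides failure to respond to reflux medication.

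| Symptom | Matching term row |
|---|---|
| Difficulty swallowing | None |
| Chest pain | None |
| Persistent heartburn | Abdominal upset, only if coded as dyspepsia |
| Upper abdominal pain | None stated; abdominal upset groups dyspepsia or nausea |

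Three of the four match no listed term. The home log (protocol Supplement 2) has a box for nausea or upset stomach and one for other symptoms, but none for swallowing difficulty, chest pain or heartburn.

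**Step 3: whether the reason for stopping is available.** SAP 9.1 takes disposition from the field for why the patient came off the study. A child taken off OIT but kept in the study need not appear there. The data that protocol 7.1 lists for collection when OIT is discontinued are the skin test and serum markers. The documents do not show a field for why OIT was stopped.

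**Step 4: timing.** Table 3.3 has two phases: the initial escalation visit, and the later escalation visits with home doses. A diagnosis made after OIT stops has no clear place in either.

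**Step 5: how much a row could tell us.** Inputs are n = 10 (protocol 9.2) and the cited 3-4%. Applying that rate to this short exposure is an assumption.

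- Expected cases: 10 × 0.03 = 0.3; 10 × 0.04 = 0.4.
- Chance of at least one: 1 − 0.97^10 = 0.263; 1 − 0.96^10 = 0.335.
- None observed: two-sided 95% Clopper-Pearson upper bound 1 − 0.025^(1/10) = 0.308; one-sided 1 − 0.05^(1/10) = 0.259.
- One observed: 1/10 = 10%, two-sided 95% interval 0.3% to 44.5%.

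Zero cases would leave an upper bound far above 3-4%, so the row could not show a lower rate than with roasted peanut.

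**The case against.** The strongest reply is that EoE is not lost. SAP 11.1 reports every AE that affects at least one patient, protocol 7.1 requires new clinically relevant findings to be reported as AEs, and step 1 shows that a recorded EoE term is named in at least three tables. That stands. A reader might infer that an EoE case would appear in no AE table; the documents do not support this. The gap is in Table 3.3 and, for suspected cases, in the lack of any link between symptom terms and the stopping criterion.

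A reader might also infer that EoE symptoms are moved into abdominal upset. The SAP has no such rule: only heartburn coded as dyspepsia could go there, and no text says that it will be.

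Protocol 8.3.8 says of events of special interest, "This is not applicable to our study". It is tempting to call this the source of the omission. That section belongs to AE reporting and does not govern the SAP's term list, so it needs no edit for this purpose.

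Other points on that side also stand. Table 3.3 counts events by severity and treatment, so an EoE event within its phases could be counted there without being named. The documents give an EoE count for only one of the three comparators. The mock table was not available to check. With 0.3-0.4 expected cases, the information gained is small. None of this supplies the missing row.

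**Conclusion.** The point holds as a minor improvement. By the SAP's own rule, the descriptive comparison that serves the secondary objective has no row for EoE. Because the stop is triggered by symptoms and specialist work-up is only considered, a suspected case may never carry an EoE term. This last step is a possibility left open by the text; the plan does not say that it will happen.

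The documents do not support the stronger conclusion that the boiled product would be presented as free of EoE, since a recorded diagnosis would be named elsewhere. The 26-34% chance of any case and the bound of about 31% for 0/10 rest on 10 children, and the former also on carrying the cited 3-4% over to a short exposure. The documents give no rate for suspected EoE under the symptom criterion.

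**What to change.** In SAP 11.1.2, make EoE an explicit exception to the limit on terms, and add a patient-level entry to Tables 3.1 and 3.3 with two separate lines:

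- EoE diagnosis recorded as an AE.
- OIT stopped for suspected EoE under protocol 7.1.

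Count each child once, and include events found after OIT stops. Give the comparators' EoE counts where they are published, and say so where they are not. Label the entry descriptive and report the exact interval beside it.

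Take the suspected count from the AE and study-drug records. Before relying on it, confirm that the forms capture the reason for stopping OIT as well as the reason for leaving the study.

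Making the change in 11.1.2 leaves the eleven-term list in SAP 5.2 matched to the protocol's secondary endpoint. The cost is a short SAP revision and two table lines, plus a data query or form field if the reason for stopping OIT is not captured. The downside is that suspected cases are not like-for-like with published EoE counts and could make the boiled product look worse, so the two lines must not be added together. No change to the clinical stopping rule is proposed.

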11.1.3 ClinicalTrials.gov 'Other (Not Including Serious) Adverse Events' table

The adverse event term list will include all preferred terms recorded for at least one patient, listed alphabetically. AEs which meet SAE Criteria will be excluded from the calculations for this table. (Refer to mock Table 3.4.)

11.2 Deaths, Serious Adverse Events and other Significant Adverse Events

11.2.1 Patient- and dose-level summary AE tables

SAEs will be included in the patient- and dose-level summary AE tables described in section 11.1.1 as a subset of the AEs.

11.2.2 ClinicalTrials.gov 'Serious Adverse Events' table

The adverse event term list will include all preferred terms recorded for at least one patient and meeting SAE criteria, listed alphabetically. (Refer to mock Table 3.5.)

11.2.3 ClinicalTrials.gov mortality table

The total number of patients and the number of patients who died due to AEs will be presented. (Refer to mock Table 3.6.)

11.3 Concomitant Medications

Current medications (listed alphabetically) will be summarized by medication name (as recorded on the concomitant medication CRF), the number of patients who reported using each medication at least once, and the total number of occurrences of use of the medication. The ITT population (all enrolled patients) will be used for this analysis. (Refer to mock Table 3.7.)

11.4 Other Safety Measures

Vital signs. For each patient, general appearance and vital signs will be listed at each study visit. The ITT population (all enrolled patients) will be used for this analysis. (Refer to mock Table 3.8.)

Accidental peanut consumption. All reported incidents of accidental peanut consumption will be

listed, sorted by patient number and time from initial dose escalation visit. Patients with no accidental peanut consumption will not be listed in the table. The ITT population (all enrolled patients) will used for this analysis. (Refer to mock Table 3.9.)

Spirometry. Spirometry was performed at the physician's discretion per protocol. When performed, spirometry results at enrollment/baseline, exit DBPCFC, and any other visits will be listed for each patient in a single table. The ITT population (all enrolled patients) will used for this analysis. (Refer to mock Table 3.10.)

Peak flow. Peak flow was performed at the physician's discretion per protocol. When performed, peak flow results at each visit will be listed for each patient in a single table. The ITT population (all enrolled patients) will used for this analysis. (Refer to mock Table 3.11.)

12 Reporting Conventions

P-values greater than 0.01 will be reported to 2 decimal places, p-value between 0.01 and 0.001 inclusive will be reported to 3 decimal places, and p-values less than 0.001 will be reported as “<0.001”. Quantiles, such as median, quartiles, minimum, and maximum will use the same number of decimal places as the original data. Percentages will be reported to one-tenth of a percent, with values less than one-tenth of a percent reported as “<0.1” and zero percent reported as 0. FAQLQ subscale and summary scores will be reported to one decimal place. All other statistics will be reported to one decimal place greater than the original data.

13 Quality Assurance of Statistical Programming

All data, code, and study information will be stored on Cleveland Clinic Lerner Research Institute's password protected servers. Each biostatistician's final code, log files, output, and derived datasets will be saved separately within a shared project directory. At the time of writing, all analyses will be performed on SAS 9.4 software via SAS Studio (SAS Institute, Cary, NC) installed on a Linux platform on the Lerner Research Institute's servers. [name], MS and [name], MS, or similarly-qualified biostatisticians in the Department of Quantitative Health Sciences at Cleveland Clinic, will independently produce the tables listed in the Statistical Analysis Plan and compare the results, and the trial statistician will review code and output as necessary.

14 Listing of Tables

Background and demographic data

Table 1.1 Disposition of patients.

Table 1.2 Analysis populations.

Table 1.3 Demographics and baseline characteristics.

Table 1.4 Timing of study visits (ITT population).

Efficacy endpoints

Table 2.1 Primary endpoint: Response to treatment (ITT population).

Table 2.2 Listing of oral food challenge results by patient (ITT population).

Table 2.3 Summary of changes in maximum tolerated dose and cumulative tolerated dose, from initial OFC to exit DBPCFC (Efficacy population, N=X).

Table 2.4 Summary of changes in serum markers of sensitization and tolerance to peanut (Modified Efficacy population for immune response, N=X).

Table 2.5 Summary of changes in parent-reported Food Allergy Quality of Life (FAQLQ-PF) scores (Modified Efficacy Population for FAQLQ-PF).

Table 2.6 Summary of changes in child-reported Food Allergy Quality of Life (FAQLQ-TF) scores (Modified Efficacy Population for FAQLQ-TF).

Safety endpoints

Table 3.1 Patient-level summary of Adverse Events (AEs) and Serious Adverse Events (SAEs) (Safety Population).

Table 3.2 Dose-level summary of Adverse Events (AEs) and Serious Adverse Events (SAEs) (Safety Population).

Table 3.3 Comparison of Adverse Events (AEs) and Serious Adverse Events (SAEs) to published data (Safety Population).

Table 3.4 ClinicalTrials.gov reporting requirement 'Other (Not Including Serious) Adverse Events' (Safety Population).

Table 3.5 ClinicalTrials.gov reporting requirement 'Serious Adverse Events' (Safety Population).

Table 3.6 ClinicalTrials.gov reporting requirement for mortality (ITT population).

Table 3.7 Summary of concomitant medications (ITT population).

Appendix I: Mock Tables.
